6.5 RANDOMIZATION

After successful enrollment, the patient will be automatically randomized in a 1:1 ratio to one of two arms through the eCRF system: "Anatomical" arm (PVI) or "Tailored" arm (Dispersion + smart-PVI). Randomization will be stratified in order to balance the treatment arms in terms of subjects with persistent AF (< 12 months) and long-standing persistent AF (≥ 12 months). Subjects will not be informed of their randomization assignment.

6.6 TREATMENT MASKING

Special care will be taken to ensure that the patient will be blinded to his/her randomization assignment throughout the study. Patient unblinding will be documented as a non-important deviation. Moreover, a blind rhythm monitoring is planned: all ECG recordings for long-term effectiveness endpoints (Holter, TTM and 12-lead ECG) will be analyzed and adjudicated blindly by an independent ECG core lab. Subjects will be asked at the 12-month visit to guess which arm of the study they are in.

6.7 STUDY STOPPING RULES

Premature termination of the study may occur motivated by a general decision (Ethics Committees, Institutional Review Boards, regulatory Competent Authorities, Data Safety Monitoring Board, Steering Committee) for safety reasons related to the use of the device or study procedures.

6.8 MEASURES TAKEN TO MINIMIZE BIAS

Several measures are incorporated into the study design to help minimize study bias as follows:

- This is a multi-center trial to help ensure that investigator or site or subject enrollment bias is minimized. Selection of subjects will be made from the Investigator's usual subject load. Consecutively eligible subjects should be enrolled into the study.
- 2) This document specifies appropriate statistical methods to ensure that bias is minimized.
- 3) Standardized and validated case report forms will be used to collect data during the study.
- 4) Steps to ensure blinding to treatment received have been taken (see Section 6.6)

6.9 CORRECTION FOR MULTIPLE-TESTING

For the two secondary efficacy endpoints, the same variable will be observed after up to two procedures (one or two procedures), or after a single procedure. Given the potential number of patients receiving a second ablation procedure (between 22% and 33%¹), the variable for both secondary efficacy endpoints will be the same for most patients, meaning that the two variables will be highly correlated. The third secondary endpoint relates to safety, and is therefore of a different nature. Consequently, no correction for multiple testing will be applied for secondary endpoints.

7 Changes from protocol

Primary endpoint hypothesis in the protocol was wrongly based on the effect size observed in a previous study and used in the sample size estimation (delta 15%, HR = 0.547). The study is powered to detect such an effect size. The tested hypotheses were corrected to H0: S1(t) = S2(t) and HA: S1(t) > S2(t).

The gatekeeping approach for secondary endpoints was abandoned. There are 3 secondary endpoints of different nature (2 highly-correlated efficacy, 1 safety) and therefore no multiple-testing correction will be applied.

8 References

- 1. Verma, A. et al. "Approaches to catheter ablation for persistent atrial fibrillation." New England Journal of Medicine 372 (2015): 1812–1822.
- 2. Fink, T. et al. "Stand-alone pulmonary vein isolation versus pulmonary vein isolation with additional substrate modification as index ablation procedures in patients with persistent and long-standing persistent atrial fibrillation: the randomized alster-lost-AF Trial (ablation at St. Georg hospital for long-standing persistent atrial fibrillation)." Circ Arrhythm Electrophysiol 10, (2017).
- Mehta, Cyrus R., and Stuart J. Pocock. "Adaptive increase in sample size when interim results are promising: a practical guide with examples." Statistics in medicine 30.28 (2011): 3267-3284.

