#### 6.5.2 – Other secondary and exploratory endpoints

For all other survival data, one-sided and two-sided Log-Rank test will be applied at a significance level of 0.05 (secondary/exploratory endpoints 2-9). The secondary efficacy endpoints will be evaluated in a pre-specified order following a gatekeeping approach so that subsequent endpoints will be evaluated if and only if the previous endpoint was found to achieve statistical significance. Thus, no correction for multiple testing will be required. Further details including the ordering of endpoints will be provided in the statistical analysis plan (SAP).

For quality of life (endpoint 10), a linear mixed model for repeated data will be used to examine the difference between groups over time.

For all other endpoints:

The continuous variables will each be analyzed by a Student's t-test, and equivalent non-parametric method, the Wilcoxon–Mann–Whitney test, will be used in case of violation of the normality assumption. Chi-square test or Fisher exact test will be used for the categorical data.

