4.3.1 Secondary Analysis

The secondary endpoint analyses will consist of the following:

Two tests of the primary endpoint in the mITT population, but expanded to be defined as freedom from AF/AT, with or without AADs, 12 months after one or two procedures. A superiority hypothesis will be tested using a Cox proportional hazards model with randomization group, AF duration, and AF/AT strata as fixed effects, with a one-sided alpha level of 0.025:

Both analyses under will be evaluated according to the following hypotheses:

$$H_0$$
: $S_1(t) = S_2(t)$

$$H_A$$
: $S_1(t) > S_2(t)$,

where $S_1(t)$ and $S_2(t)$ represent the survival functions for the Tailored and Anatomical arms, respectively, at any given time t. If the null hypotheses for each of the tests is rejected, the following superiority statements will be considered on behalf of each endpoint:

- 1. Tailored ablation is superior to anatomical with respect to freedom from AF/AT, with or without AADs, 12 months after one or two procedures.
- 2. Tailored ablation is superior to anatomical with respect to freedom from AF/AT, with or without AADs, 12 months after one procedure.

Similarly to the primary endpoint analyses, Cox Proportional hazards regression models will be fit and assessed for goodness-of-fit. Then to test each null hypothesis, one-sided Log-Rank Tests will be. Just like under the primary analysis, the p-value from the one-sided Log-Rank Test run under each Cox Proportional hazards model will ultimately be what is used to either reject (p < 0.025) or fail to reject ($p \ge 0.025$) the null hypotheses above. Both Cox models will be conducted in the mITT population.

Kaplan-Meier plots will be generated for each endpoint, to visually display the differences among the survival distributions of the Tailored and Anatomical arms, respectively, with each plot accommodated by the p-value generated from their respective one-sided Log-Rank test.

3. The composite adverse event (AE) rate defined as the number of AEs per month occurring in each treatment arm from time of index procedure through to 12-month follow-up, where composite AEs are defined by either death, a cerebrovascular event, or any serious procedure-related adverse event, will be conducted. in the Safety population (see Section 4.5, Safety Endpoints below).

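### The SAP drops ordered testing of the two secondary efficacy endpoints because they are correlated, but correlation below 1 leaves the chance of a false superiority statement above the one-sided 0.025 used for each

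*SAP*

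**What the plan says.** Protocol 6.5.2 puts the secondary efficacy endpoints in a pre-specified order under which "subsequent endpoints will be evaluated if and only if the previous endpoint was found to achieve statistical significance", and concludes from this that no correction is needed. It leaves the order to the SAP. For the other survival endpoints it says that "one-sided and two-sided Log-Rank test will be applied at a significance level of 0.05".

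SAP section 7 records the change: "The gatekeeping approach for secondary endpoints was abandoned". SAP 6.9 gives two reasons. Between 22% and 33% of patients may have a second ablation, so the two efficacy variables coincide for most patients and are highly correlated; and the third secondary endpoint concerns safety. It ends: "Consequently, no correction for multiple testing will be applied for secondary endpoints".

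SAP 4.3.1 tests the two AF/AT endpoints "with a one-sided alpha level of 0.025" and provides that, on rejection, "the following superiority statements will be considered on behalf of each endpoint". The second statement reads: "Tailored ablation is superior to anatomical with respect to freedom from AF/AT, with or without AADs, 12 months after one procedure". SAP section 3 says that the analyses may support regulatory submissions and that the SAP prevails over the protocol.

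**The concern.** In the protocol, the fixed order was the reason that no correction was needed. The SAP removes the order and keeps the conclusion, with correlation as the new reason. Correlation can do that work only if it is perfect. Short of that, two separate chances to declare superiority carry more risk than one.

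The share of patients with identical data also overstates the correlation of the tests. Log-rank information comes from events, and under Protocol 5.3.6 re-ablation is a treatment for recurrence. The patients with a second procedure are therefore drawn largely from those who have events on the single-procedure endpoint.

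The remaining reason, that the third endpoint is safety, says nothing about the two efficacy statements. In addition, neither SAP 4.3.1 nor 6.9 makes these statements depend on the primary result, so as written one could be issued after a failed primary.

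At stake are two formal secondary claims. The primary test is not affected.

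**Working it through.** **The plan's own figures.** Neither document states a family error, so there is none to reproduce. The related figure is the sample size, which confirms that the plan works at one-sided 0.025 (SAP 4.2.2).
- HR = ln(0.77)/ln(0.62) = 0.5467, matching the stated 0.547.
- Schoenfeld events = 4 × (1.960 + 0.842)² / (ln 0.5467)², rounded up to 87.
- Average event proportion = (0.38 + 0.23)/2 = 0.305, so N = 87/0.305, rounded up to 286. This is close to the stated 292.

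**Inputs for the family error.** There are two tests, each one-sided at 0.025 (critical value 1.96), each with its own statement and no correction (SAP 4.3.1 and 6.9). The correlation ρ between the test statistics is not given and is an assumption here.

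**Formula.** With both nulls true, the chance of at least one false statement is 1 − Φ₂(1.96, 1.96; ρ), where Φ₂ is the bivariate normal distribution function. At ρ = 0 this is 1 − 0.975² = 0.0494, the maximum for non-negative correlation.

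| ρ (assumed) | Chance of at least one false statement | Ratio to 0.025 |
|---|---|---|
| 0 | 0.0494 | 1.98 |
| 0.4 | 0.0466 | 1.86 |
| 0.5 | 0.0454 | 1.82 |
| 0.7 | 0.0417 | 1.67 |
| 0.8 | 0.0390 | 1.56 |
| 0.9 | 0.0352 | 1.41 |
| 0.95 | 0.0323 | 1.29 |
| 1 | 0.0250 | 1.00 |

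Only ρ = 1 returns 0.025.

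**Which ρ is plausible.**
- Taking ρ as the share of patients without a second procedure (1 − 0.33 = 0.67 to 1 − 0.22 = 0.78) gives 0.042 to 0.040.
- In terms of events: if 35% to 55% of patients have an AF/AT recurrence (assumed), a second-procedure share of 22% to 33% equals between 22/55 = 40% and 33/35 = 94% of the single-procedure events.
- Paired log-rank tests were simulated under the null with 292 patients and target second-procedure shares of 22% and 33%. Assumptions: 40% to 60% free of AF/AT after one procedure, 50% to 70% free over nine months after a second, and the first recurrence not counted once a second procedure is done. Correlations were about 0.41 to 0.73. In the formula these give about 0.047 down to 0.041.

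**With a fixed sequence.** A false statement requires rejecting the first true null in the order at 0.025. The family error over the ordered tests is therefore at most 0.025, whatever ρ is.

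**The case against.** The strongest reply is that the SAP does not loosen the protocol. Protocol 6.5.2 set 0.05 for these endpoints; gatekeeping at one-sided 0.05 would allow a family error of 0.05, and the SAP's unadjusted pair cannot exceed 0.0494. The change is also declared openly in SAP section 7, and the SAP prevails. All of this stands. It does not rescue the stated reason. The SAP chose 0.025 for these claims, and in 4.4.1 it describes one-sided 0.05 as less stringent and keeps it for exploratory endpoints.

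Several stronger readings are tempting but not supported.

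- A reader might infer that the family error is 0.043 to 0.047. That needs ρ of about 0.64 down to 0.37, and the documents give no coefficient. If highly correlated means 0.7 to 0.9, the figure is 0.042 to 0.035.
- A reader might infer that a promised 0.025 family error was broken. Neither document promises one for the secondary endpoints.
- A reader might infer that the SAP removed a gate on the primary. Protocol 6.5.2 orders the secondary efficacy endpoints but does not expressly make the primary the first gate. What can be said is that the SAP has no such gate.
- A reader might infer that the two endpoints differ in every patient with a second procedure. Under SAP 6.2 a repeat procedure after month 9 is disregarded for the multiple-procedure endpoints, and a patient who recurs again has an event on both endpoints, at different times.

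**Conclusion.** The concern holds in a limited form. High correlation does not make multiplicity control unnecessary, and the SAP gives no other reason that bears on its two efficacy statements. With both nulls true, the chance of at least one false statement is above 0.025 for any correlation below 1 and at most 0.0494 for non-negative correlation. It is about 0.035 to 0.047 (1.4 to 1.9 times 0.025) for ρ from 0.9 down to 0.4. The bounds follow from the documents; the narrower range rests on the assumed correlation.

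This is a weak justification for a disclosed change. It is not a hidden contradiction, and the primary analysis and its power are untouched. It should be corrected because the SAP attaches formal superiority statements to these tests and foresees regulatory use.

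**What to change.** Specify one fixed sequence in SAP 4.3.1 and 6.9, each test at one-sided 0.025:

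1. the primary endpoint;
2. freedom from AF/AT after one or two procedures;
3. freedom from AF/AT after one procedure.

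Steps 2 and 3 follow the order in SAP 4.3. Formal superiority claims stop at the first non-significant result, and later endpoints are reported with estimates and confidence intervals only. Delete the argument that correlation makes control unnecessary, and update section 7 to match. The SAP should present this as a new rule: it combines the protocol's gatekeeping principle with the SAP's level, and the protocol itself fixed neither this order nor 0.025.

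The cost is SAP wording. No alpha is split, so the primary test and its power do not change. The downside is that a later endpoint cannot be claimed if an earlier one fails. The protocol had accepted that principle for its secondary endpoints, and between the two AF/AT endpoints the loss is small if they are as correlated as the SAP says. By comparison, Bonferroni or Holm would start at 0.0125 per test. A correlation-adjusted level would be about 0.0135 to 0.0175 for ρ of 0.5 to 0.9, but it needs a coefficient that the documents do not give.
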